5.1.3 Subject Exclusion Criteria

The subject must be excluded from participating in the trial if the subject:

1. Is currently participating and receiving study therapy or has participated in a study of an investigational agent and received study therapy or used an investigation device within 4 weeks of the first dose of treatment.
2. Is either:

- 1) BRAF mutation-positive and has received prior systemic therapy for metastatic or advanced melanoma.

Note: Prior adjuvant or neoadjuvant therapy is allowed (i.e., does not count as prior systemic therapy) as long as that therapy did not include compounds targeting PD-1, PD-L1, BRAF, or MEK. Treatment must end at least 4 weeks prior to randomization. Prior adjuvant therapy with anti-CTLA-4 will only be permitted if relapse did not occur during treatment or within 6 months of treatment discontinuation.

or

- 2) BRAF mutation-negative and has received >1 prior systemic therapy for metastatic melanoma.

Note: Prior adjuvant or neoadjuvant therapy does not count as prior line of systemic therapy, but should not include compounds targeting PD-1, PD-L1, BRAF, or MEK. Treatment must end at least 4 weeks prior to randomization.

- The BRAF exclusion criterion does not apply to solid tumor subjects in Parts 4 and 5 (dose confirmation only).

3. Has received prior therapy with compounds targeting the PD-1, PD-L1, BRAF, MEK or other molecules in the MAPK pathway.

Note: Examples of BRAF inhibitors include, but are not limited to, dabrafenib and vemurafenib. An example of a MEK inhibitor includes, but is not limited to, trametinib.

4. Is BRAF mutation-positive and has received prior systemic therapy with ipilimumab or other CTLA-4 blocking antibodies.

5. Has had chemotherapy, radioactive, or biological cancer therapy within four weeks prior to the first dose of trial treatment, or who has not recovered to CTCAE Grade 1 or better from the clinically significant AEs due to cancer therapeutics administered more than four weeks prior to the first dose of trial treatment.
6. Is expected to require any other form of systemic or localized antineoplastic therapy while in study.
7. Has a known additional malignancy that is progressing or requires active treatment. Exceptions include early stage cancers (carcinoma in situ or stage 1) treated with curative intent, basal cell carcinoma of the skin, squamous cell carcinoma of the skin, in situ cervical cancer, or in situ breast cancer that has undergone potentially curative therapy. For dabrafenib-containing treatment regimens in this study, subjects with any malignancy with confirmed activating RAS mutation are excluded.

Note: Prospective RAS testing is not required. However, if the results of previous RAS testing are known, they must be used in assessing eligibility.

8. Has known active central nervous (CNS) metastases and/or carcinomatous meningitis. Subjects with previously treated brain metastases may participate provided they are stable (without evidence of progression by MRI for at least four weeks prior to the first dose of trial treatment and any neurologic symptoms have returned to baseline), have no evidence of new or enlarging brain metastases, and are off systemic steroids for at least two weeks.
9. Has an active infection requiring systemic therapy.
10. Has an active autoimmune disease, or a documented history of autoimmune disease, or a syndrome that requires systemic steroids or immunosuppressive agents. Subjects with vitiligo or resolved childhood asthma/atopy would be exception to this rule. Subjects that require intermittent use of bronchodilators or local steroid injections are not excluded from the study. Subjects with hypothyroidism stable on hormone replacement are not excluded from the study.
11. Has previously had a severe hypersensitivity reaction to treatment with another monoclonal antibody (mAb).
12. Is on chronic systemic steroid therapy (>10 mg/day prednisone or equivalent) within two weeks before the planned date for first dose of study treatment or on any other form of immunosuppressive medication. (Subjects that are expected to require premedication with corticosteroid for pembrolizumab will not be eligible for this study.)
13. Currently uses a prohibited medication as described in Section 5.5.2.

14. Has history or evidence of cardiovascular risk including any of the following:

- 1) Current LVEF < LLN as determined by echocardiogram;
- 2) A QT interval corrected for heart rate using the Bazett's formula (QTcB; [90]) ≥ 480 msec;
- 3) A history or evidence of current clinically significant uncontrolled arrhythmias;

Exception: Subjects with atrial fibrillation controlled for > 30 days prior to randomization are eligible.
- 4) A history (within 6 months prior to randomization) of acute coronary syndromes (including myocardial infarction or unstable angina), coronary angioplasty or stenting;
- 5) A history or evidence of current \geq Class II congestive heart failure as defined by the New York Heart Association (NYHA) guidelines [91];
- 6) Treatment refractory hypertension defined as a blood pressure of systolic > 140 mmHg and/or diastolic > 90 mm Hg which cannot be controlled by anti-hypertensive therapy;
- 7) Subjects with intra-cardiac defibrillators;
- 8) Abnormal cardiac valve morphology (\geq grade 2) documented by echocardiogram (subjects with grade 1 abnormalities [i.e., mild regurgitation/stenosis] can be entered on study). Subjects with moderate valvular thickening should not be entered in study.

15. Has uncorrectable electrolyte abnormalities (e.g. hypokalaemia, hypomagnesaemia, hypocalcaemia), long QT syndrome or taking medicinal products known to prolong the QT interval.

16. Has known history of prior or current retinal vein occlusion (RVO).

Note: In the event history of RVO is not known, an ophthalmic exam is required.

17. Has known immediate or delayed hypersensitivity reaction or idiosyncrasy to drugs chemically related to the study treatments, their excipients, and/or dimethyl sulfoxide (DMSO).

18. Has had an allogeneic tissue/solid organ transplant, prior stem cell or bone marrow transplant.

19. Has a history of (non-infectious) pneumonitis that required steroids or current pneumonitis.
20. Has known history of Human Immunodeficiency Virus (HIV) (HIV 1/2 antibodies).
21. Has a known history of or is positive for Hepatitis B (HBsAg reactive) or Hepatitis C (HCV RNA [qualitative] is detected).

Note: In those countries, where standard of care uses only Hepatitis C antibody testing as evidence of status of Hepatitis C, HCV RNA testing is not required.

22. Has received a live vaccine within 30 days prior to first dose.
23. Has a known psychiatric or substance abuse disorder that would interfere with the subject's ability to cooperate with the requirements of the trial.
24. Has a clinical history suggestive of a condition which could impact the safety or efficacy of the subject in the study.
25. Is, at the time of signing informed consent, a regular user (including "recreational use") of any illicit drugs or had a recent history (within the last year) of substance abuse (including alcohol).
26. Is pregnant or breastfeeding, or expecting to conceive or father children within the projected duration of the trial, starting with the screening visit (Visit 1) through 120 days after the last dose of trial treatment.
27. Is or has an immediate family member (spouse or children) who is investigational site or sponsor staff directly involved with this trial, unless prospective IRB approval (by chair or designee) is given allowing exception to this criterion for a specific subject.

5.2 Trial Treatment(s)

The treatments to be used in this trial are outlined below in. A cycle of treatment in this protocol is defined as six weeks, except as noted in the table.

Table 9 Trial Treatment

Drug	Dose/Potency	Dose Frequency	Route of Administration	Regimen/Treatment Period	Use
Pembrolizumab	1mg/kg*	Q3W	IV infusion	Days 1 and 22 of each cycle in Parts 1, 2, or 3	Experimental
Pembrolizumab	2mg/kg	Q3W	IV infusion	Days 1 and 22 of each cycle in Parts 1, 2, or 3	Experimental
Pembrolizumab	200 mg	Q3W	IV infusion	Days 1 and 22 of each cycle in Parts 4 or 5, with the exception of Cycle 1**	Experimental
Placebo (saline IV)	--	Q3W	IV infusion	Days 1 and 22 of each cycle	Experimental
Trametinib	1.5mg*	1.5mg QD	Oral	Day 1 up until study treatment discontinuation	Experimental
Trametinib	2mg	2mg QD	Oral	Day 1 up until study treatment discontinuation	Experimental
Dabrafenib	150mg*	75mg BID	Oral	Day 1 up until study treatment discontinuation	Experimental
Dabrafenib	200mg*	100mg BID	Oral	Day 1 up until study treatment discontinuation	Experimental
Dabrafenib	300mg	150mg BID	Oral	Day 1 up until study treatment discontinuation	Experimental

*Dose/Potency activated only in the event dose reduction required.

**Cycle 1 in Parts 4 and 5 are longer in length due to trametinib run-in of two or four weeks.

For dosing regimens initiating with four weeks of trametinib monotherapy, pembrolizumab dosing occurs on Days 29 and 50. For dosing regimens initiating with two weeks of trametinib monotherapy, pembrolizumab dosing occurs on Days 15 and 36.

Please note, the term ‘study treatment’ is used throughout the protocol to describe any combination of products received by the subject as per the protocol design. Study treatment may therefore refer to the individual study treatments or a combination of those study treatments.

Trial treatment should begin on the day of randomization or as close as possible to the date on which the subject is allocated/assigned.

5.2.1 Dose Selection/Modification

5.2.1.1 Dose Selection

The rationale for selection of doses to be used in this trial is provided in Section 4.0 – Background & Rationale.

In Parts 1, 2, and 3 of this trial, the dose amount required to prepare the pembrolizumab infusion solution will be based on the subject's weight in kilograms (kg). In Parts 4 and 5, a flat dose (independent of the subject's weight) for pembrolizumab infusion is required. Details on the dose calculation, preparation and administration are provided in the Pharmacy Manual.

Trametinib and dabrafenib will be administered as per the approved product labels.

5.2.1.2 Dose Modification

It should be noted that for dose modifications in Part 3 of the study, changes could occur for either pembrolizumab or placebo (saline IV) in combination with trametinib and dabrafenib, depending on the study arm assignment. Detailed dose modification and toxicity management guidelines for each study treatment are provided in Section 5.6 ([Table 16](#) to [Table 35](#)).

5.2.1.2.1 Dose Modification and Toxicity Management Guidelines for Pembrolizumab

Dose modification and toxicity management for immune-related AEs associated with pembrolizumab

AEs associated with pembrolizumab exposure may represent an immunologic etiology. These immune-related AEs (irAEs) may occur shortly after the first dose or several months after the last dose of pembrolizumab treatment and may affect more than one body system simultaneously. Therefore, early recognition and initiation of treatment is critical to reduce complications. Based on existing clinical study data, most irAEs were reversible and could be managed with interruptions of pembrolizumab, administration of corticosteroids and/or other supportive care. For suspected irAEs, ensure adequate evaluation to confirm etiology or exclude other causes. Additional procedures or tests such as bronchoscopy, endoscopy, skin biopsy may be included as part of the evaluation. Based on the severity of irAEs, withhold or permanently discontinue pembrolizumab and administer corticosteroids. Dose modification and toxicity management guidelines for irAEs associated with pembrolizumab are provided in [Table 10](#) below and in Section 5.6. See Section 5.6 for detailed supportive care guidelines, including use of corticosteroids for specific AEs.

Table 10 Dose Modification and Toxicity Management Guidelines for Immune-related AEs Associated with Pembrolizumab

General instructions:				

 1. Corticosteroid taper should be initiated upon AE improving to Grade 1 or less and continue to taper over at least 4 weeks. 2. For situations where pembrolizumab has been withheld, pembrolizumab can be resumed after AE has been reduced to Grade 1 or 0 and corticosteroid has been tapered. Pembrolizumab must be permanently discontinued if AE does not resolve within 12 weeks of last dose or corticosteroids cannot be reduced to ≤ 10 mg prednisone or equivalent per day within 12 weeks. 3. For severe and life-threatening irAEs, IV corticosteroid should be initiated first followed by oral steroid. Other immunosuppressive treatment should be initiated if irAEs cannot be controlled by corticosteroids. 				
Immune-related AEs	Toxicity grade or conditions (CTCAEv4.0)	Action taken to pembrolizumab	irAE management with corticosteroid and/or other therapies	Monitor and follow-up
Pneumonitis (see also Table 22)	Grade 2	Withhold	
 • Administer corticosteroids (initial dose of 1-2 mg/kg prednisone or equivalent) followed by taper 	
 • Monitor participants for signs and symptoms of pneumonitis • Evaluate participants with suspected pneumonitis with radiographic imaging and initiate corticosteroid treatment • Add prophylactic antibiotics for opportunistic infections
	Grade 3 or 4, or recurrent Grade 2	Permanently discontinue		
Diarrhea / Colitis (see also Table 18)	Grade 2 or 3	Withhold	
 • Administer corticosteroids (initial dose of 1-2 mg/kg prednisone or equivalent) followed by taper 	
 • Monitor participants for signs and symptoms of enterocolitis (ie, diarrhea, abdominal pain, blood or mucus in stool with or without fever) and of bowel perforation (ie, peritoneal signs and ileus). • Participants with \geq Grade 2 diarrhea suspecting colitis should consider GI consultation and performing endoscopy to rule out colitis. • Participants with diarrhea/colitis should be advised to drink liberal quantities of clear fluids. If sufficient oral fluid intake is not feasible, fluid and electrolytes should be substituted via IV infusion.
	Grade 4	Permanently discontinue		

Immune-related AEs	Toxicity grade or conditions (CTCAEv4.0)	Action taken to pembrolizumab	irAE management with corticosteroid and/or other therapies	Monitor and follow-up
AST / ALT elevation or Increased bilirubin See also Section 5.6.1.1.15	Grade 2	Withhold See also Table 30	
 Administer corticosteroids (initial dose of 0.5-1 mg/kg prednisone or equivalent) followed by taper 	
 Monitor with liver function tests (consider weekly or more frequently until liver enzyme value returned to baseline or is stable)
	Grade 3 or 4	Permanently discontinue Note: For Grade 3 events see Table 30 for detailed management and dose modification guidelines based on specific hepatic laboratory abnormalities	
 Administer corticosteroids (initial dose of 1-2 mg/kg prednisone or equivalent) followed by taper 	
Type 1 diabetes mellitus (T1DM) or Hyperglycemia See also Section 5.6.1.1.6	Newly onset T1DM or Grade 3 or 4 hyperglycemia associated with evidence of β -cell failure	Withhold	
 Initiate insulin replacement therapy for participants with T1DM Administer anti-hyperglycemic in participants with hyperglycemia 	
 Monitor participants for hyperglycemia or other signs and symptoms of diabetes.
Hypophysitis See also Table 19	Grade 2	Withhold	
 Administer corticosteroids and initiate hormonal replacements as clinically indicated. 	
 Monitor for signs and symptoms of hypophysitis (including hypopituitarism and adrenal insufficiency)
	Grade 3 or 4	Withhold or permanently discontinue ¹		
Hyperthyroidism See also Section 5.6.1.1.6	Grade 2	Continue	
 Treat with non-selective beta-blockers (eg, propranolol) or thionamides as appropriate 	
 Monitor for signs and symptoms of thyroid disorders.
	Grade 3 or 4	Withhold or permanently discontinue ¹		

Immune-related AEs	Toxicity grade or conditions (CTCAEv4.0)	Action taken to pembrolizumab	irAE management with corticosteroid and/or other therapies	Monitor and follow-up
Hypothyroidism See also Section 5.6.1.1.6	Grade 2-4	Continue	
 Initiate thyroid replacement hormones (eg, levothyroxine or liothyronine) per standard of care 	
 Monitor for signs and symptoms of thyroid disorders.
Nephritis and Renal dysfunction See also Table 23	Grade 2	Withhold	
 Administer corticosteroids (prednisone 1-2 mg/kg or equivalent) followed by taper. 	
 Monitor changes of renal function
	Grade 3 or 4	Permanently discontinue		
Myocarditis See also Section 5.6.1.1.12	Grade 1 or 2	Withhold	
 Based on severity of AE administer corticosteroids 	
 Ensure adequate evaluation to confirm etiology and/or exclude other causes
	Grade 3 or 4	Permanently discontinue		
All other immune-related AEs See also Section 5.6.1.3 and Table 35	Intolerable/persistent Grade 2	Withhold	
 Based on type and severity of AE administer corticosteroids 	
 Ensure adequate evaluation to confirm etiology and/or exclude other causes
	Grade 3	Withhold or discontinue based on the type of event. Events that require discontinuation include and not limited to: Guillain-Barre Syndrome, encephalitis		
	Grade 4 or recurrent Grade 3	Permanently discontinue		

1. Withhold or permanently discontinue pembrolizumab is at the discretion of the investigator or treating physician.
 
NOTE: For participants with Grade 3 or 4 immune-related endocrinopathy where withhold of pembrolizumab is required, pembrolizumab may be resumed when AE resolves to ≤ Grade 2 and is controlled with hormonal replacement therapy or achieved metabolic control (in case of T1DM).
				

With investigator and Sponsor agreement, subjects with a laboratory adverse event still at Grade 2 after 12 weeks may continue treatment in the trial only if asymptomatic and controlled. For information on the management of adverse events, see Section 5.6.1.

For subjects who experience a recurrence of the same AE(s) at the same grade or greater with rechallenge of pembrolizumab, a consultation between the Sponsor and investigator should occur to determine whether the subject should continue in the trial. **However, for a subject who experiences a recurrence of the same serious adverse event at the same grade or greater with rechallenge of pembrolizumab, the subject must discontinue pembrolizumab.**

Dose increase of pembrolizumab will not be permitted in individual subjects unless a dose level of pembrolizumab is dropped during the trial. If this occurs then those subjects who were assigned the dropped dose may switch to the remaining dose level at the discretion of the investigator.

Dose modification and toxicity management of infusion-reactions related to pembrolizumab

See Section 5.6.1.2

Other allowed dose interruption for pembrolizumab

Pembrolizumab may be interrupted for situations other than treatment-related AEs such as medical / surgical events or logistical reasons not related to study therapy. Participants should be placed back on study therapy within 3 weeks of the scheduled interruption, unless otherwise discussed with the Sponsor. The reason for interruption should be documented in the patient's study record.

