Grade 2	
 CT scan (high-resolution with lung windows) Consider frequent Chest X-ray for monitoring Clinical evaluation and laboratory work-up for infection Consult pulmonologist, consider Infectious Disease consultation Conduct in-person evaluation approximately twice per week Bronchoscopy with biopsy and/or BAL recommended Treat with systemic corticosteroids at a dose of 1 to 2 mg/kg/day prednisone or equivalent. When symptoms improve to Grade 1 or less, steroid taper (if systemic corticosteroids initiated) should be started and continued over no less than 4 weeks. 	
 Interrupt study all treatment until recovery to grade ≤ 1 Treatment with pembrolizumab may be resumed if the event improves to \leq Grade 1 within 12 weeks and corticosteroids have been reduced to the equivalent of methylprednisolone 10 mg PO daily or less. Repeat chest imaging monthly as clinically indicated. Treatment with dabrafenib and trametinib at one dose level reduction may be resumed if the event improves to \leq Grade 1 within 4 weeks; escalation to previous dose level after 4 weeks may be possible after discussion with sponsor If no recovery to grade ≤ 1 within 4 weeks or second episode of Grade 2 or higher pneumonitis on re-challenge, permanently discontinue all study treatment

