5.6.1.3 Supportive Care Guidelines for Adverse Events with an Immune-Etiology (irAEs)

Adverse events of a potential immunologic etiology (irAEs) may be defined as an adverse event of unknown etiology, associated with drug exposure and is consistent with an immune phenomenon. irAEs may be predicted based on the nature of the pembrolizumab compound, its mechanism of action, and reported experience with immunotherapies that have a similar mechanism of action. Special attention should be paid to AEs that may be suggestive of potential irAEs. An irAE can occur shortly after the first dose or several months after the last dose of treatment.

If an irAE is suspected, efforts should be made to rule out neoplastic, infectious, metabolic, toxin or other etiologic causes prior to labeling an adverse event as an irAE. Subjects who develop a Grade 2 or higher irAE should be discussed immediately with the Sponsor.

Recommendation to evaluate and manage irAEs are provided in Section 5.6.1.1.3 and Section 5.2.1.2.1, [Table 10](#). Recommendations to managing irAEs that are not detailed elsewhere in the protocol are detailed in [Table 35](#).

Table 35 General Approach to Handling irAEs

irAE	Withhold/Discontinue Pembrolizumab?	Supportive Care
Grade 1	No action	Provide symptomatic treatment
Grade 2	May withhold pembrolizumab	Consider systemic corticosteroids in addition to appropriate symptomatic treatment
Grade 3 and Grade 4	Withhold pembrolizumab Discontinue if grade 4 or grade 3 and unable to reduce corticosteroid dose to < 10 mg per day prednisone equivalent within 12 weeks of toxicity	Systemic corticosteroids are indicated in addition to appropriate symptomatic treatment. May utilize 1 to 2 mg/kg prednisone or equivalent per day. Steroid taper should be considered once symptoms improve to Grade 1 or less and tapered over at least 4 weeks.

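### Section 5.2.1.2.1 gives two different pembrolizumab rules for a non-serious recurrent irAE: Table 10 requires a permanent stop, the paragraph after it only a consultation

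*Combined protocol and SAP*

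**What the plan says.** Table 10 (Section 5.2.1.2.1) contains two recurrence rules for pembrolizumab, each with permanent discontinuation as the action:

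- Pneumonitis: "Grade 3 or 4, or recurrent Grade 2".
- All other irAEs: "Grade 4 or recurrent Grade 3".

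Neither mentions seriousness. The second row also carries a cross-reference: "See also Section 5.6.1.3 and Table 35".

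The paragraph after the table, in the same subsection, sets its own rule for rechallenge: "recurrence of the same AE(s) at the same grade or greater with rechallenge of pembrolizumab, a consultation between the Sponsor and investigator should occur". The stated purpose of the consultation is to decide whether the subject stays in the trial. A contrasting sentence then makes stopping compulsory in one case: "recurrence of the same serious adverse event at the same grade or greater with rechallenge of pembrolizumab, the subject must discontinue pembrolizumab".

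For pneumonitis, Table 22 (Section 5.6.1.1.8) has a matching rule in its Grade 2 row: "second episode of Grade 2 or higher pneumonitis on re-challenge, permanently discontinue all study treatment".

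Table 35 (Section 5.6.1.3) covers irAEs not detailed elsewhere. It discontinues pembrolizumab for Grade 4, or for Grade 3 when corticosteroids cannot be reduced in time. It does not mention recurrence.

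**The concern.** The table makes grade and recurrence the test for stopping. The paragraph makes seriousness the test. Section 7.2.4 requires every adverse event to be judged for seriousness whatever its CTCAE grade, so the two tests can separate: an event can recur at Grade 2 or 3 without being serious. An investigator who follows the table stops pembrolizumab for good. One who follows the paragraph consults the Sponsor, with the outcome open.

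What is at stake is re-exposure to pembrolizumab after an immune-related event has already come back once, which is the hazard that the two recurrence rules address. Two sites could handle the same event differently, and each could point to protocol text. Section 2.1 allows pembrolizumab in Parts 4 and 5 to run to 24 months, and Section 8.2.1 lets Part 3 subjects on the triplet continue after unblinding. Rechallenge therefore remains possible under the current text.

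**Working it through.** The plan states no figure on this point and no arithmetic applies. The check sets the rules side by side for the same subject.

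| Recurrence on rechallenge | Table 10 | Paragraph after Table 10 | Related table |
|---|---|---|---|
| Grade 2 pneumonitis, not serious | Stop pembrolizumab permanently | Consult | Table 22: stop all study treatment |
| Grade 3 irAE in the all-other row, not serious | Stop pembrolizumab permanently | Consult | Table 35: no recurrence rule |
| Either event, serious | Stop pembrolizumab permanently | Must stop pembrolizumab | No conflict |

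**Row 1.** Two tables agree against one general sentence. The paragraph is still inconsistent with them, but a site that opens the pneumonitis section will find the strict rule.

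**Row 2.** Nothing repeats the strict rule. Immune-related rash is a realistic example. Table 10 has no skin row, so such a rash falls under all other irAEs, and Section 5.6.1.1.10.1 describes rash as frequent with the kinase inhibitors and also seen with pembrolizumab. Table 25 tells the site to restart pembrolizumab once a Grade 3 rash has recovered and steroids are tapered, and to consider discontinuing it. It has no pembrolizumab rule for a second episode. The rash section refers only to Tables 24 and 25, whereas the diarrhea, pneumonitis and renal sections also point back to Table 10.

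**Row 3.** The rules agree, so the conflict is confined to non-serious recurrences.

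**Does any other text decide between them?**

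- Section 5.6.1 tells sites to use the algorithm for the treatment concerned. Both texts here are pembrolizumab rules in one subsection.
- Section 5.6.1.1.3 allows permanent discontinuation to be discussed with the Sponsor, and Section 5.6.1.3 requires immediate discussion of Grade 2 or higher irAEs. Neither says which rule governs.
- Section 5.8.1 requires treatment to stop for unacceptable adverse experiences as described in Sections 5.2.1.2 and 5.6. The table and the paragraph both lie within Section 5.2.1.2, so this does not choose between them.

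**The case against.** The strongest reply is that the two texts can both be obeyed. The paragraph never says in terms that pembrolizumab may be resumed. It asks whether the subject stays in the trial, which is a real question even after pembrolizumab stops: Section 5.6.1.1.2 lets the remaining drugs continue, and Section 5.8.1 separates stopping treatment from leaving the trial. An investigator could stop under Table 10 and consult as well. The ordinary reading that a specific table overrides a general paragraph points the same way.

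Part of this stands. The paragraph covers any recurrent adverse event, and reading it as a default that yields to Table 10 is sensible. But the protocol does not say so. The sentence that follows opens with a contrast and sets consultation against compulsory discontinuation of pembrolizumab. The natural inference is that for a non-serious recurrence pembrolizumab may continue after consultation.

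A second reply is that few recurrent Grade 3 events would be non-serious. Table 37 describes Grade 3 in terms that overlap the seriousness criteria (hospitalization, disability), and an event can also be serious as another important medical event. This stands as a limit on size: many recurrent Grade 3 events would be serious, and the texts then agree.

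A reader might infer from Table 10 alone that recurrent pneumonitis is equally exposed. The documents do not support that, because Table 22 independently requires the stop and extends it to all study treatment.

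**Conclusion.** The inconsistency is real and bounded. Both recurrence rules in Table 10 conflict with the paragraph when the recurrence is not serious. With Table 22 covering pneumonitis, the practical gap is mainly a non-serious recurrent Grade 3 irAE in the all-other row. This is more than missing detail, because two stated rules give different actions for the same subject.

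The conclusion rests on reading the paragraph's contrast as leaving pembrolizumab open after consultation, and on such events sometimes being non-serious, which Section 7.2.4 allows. The documents give neither the number of such recurrences nor the number of subjects still on pembrolizumab, so no frequency is claimed.

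Three further inferences are not supported:

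- A reader might conclude that every other Table 10 row is free of difficulty. That is not established. The hypophysitis row points to Table 19, which has its own stop after repeated interruptions, qualified by investigator discretion.
- A reader might add the 10 mg/day prednisone limits in Tables 10 and 35 as a second conflict. They differ only at exactly 10 mg/day, and the difference depends on inequality signs that would need checking in the source PDF. The point is too slight to pursue.
- A reader might suppose that the trial's conclusions are affected. They are not. Endpoints and power do not depend on which rule is followed, and Section 5.2.5 reports the Part 3 final analysis as done.

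**What to change.** At the next amendment:

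1. Begin the paragraph after Table 10 with: *Except where Table 10 or the event-specific tables require permanent discontinuation of pembrolizumab,* and leave the rest of it as it stands. Consultation then applies only to recurrences for which no stop is already required.
2. In the Grade 3 and 4 row of Table 35, add *or recurrent Grade 3* to the discontinuation triggers, so that the table cited by the all-other row carries the same rule.

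The cost is one clause and one table cell. Neither edit creates a new stopping rule, since Table 10 already contains both stops. No data collection, analysis or sample size changes.
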